14. STUDY MEDICATION COMPLIANCE AND EXPOSURE

The time from randomization to IMP discontinuation (last dose) will be summarized by treatment groups, and presented using a Kaplan-Meier plot for all patients in the FAS. Patients not dosed will have a time of 0.

In addition, estimated compliance with study IMP will be presented for the FAS by treatment groups. The patients will be grouped as compliant, i.e., those who have $\geq 80\%$ of required tablets (taken once daily) while on treatment, versus noncompliant ($<80\%$ compliance).

The percentage compliance calculation will be based on the tablet counts using the formula:

$$\text{Total \# of tablets taken} = \sum_{\text{bottles}} (100 - (\# \text{ of tablets returned}))$$

as each bottle of double-blind IMP contains 100 tablets. If a dispensed bottle is not returned, it is assumed that the patient has taken all the tablets and the number of tablets returned is set to be zero (0).

$$\% \text{compliance} = \frac{[\text{total \# of tablets taken}]}{[\# \text{ of days between last and first doses}]}$$

The percentage compliance is capped as a maximum of 100% if it exceeds 100% due to the imputation above.

Note that patients who did not receive any IMP will be counted as noncompliant (0%). In addition, if a patient did not return any bottles, he/she will also be counted as noncompliant (0%).

Exposure to the study treatment is based on the duration (in years) between the last and first doses, and will be presented for the SAS by treatment groups. Exposure will also be presented for patients in the SAS with baseline ezetimibe use.

15. EFFICACY ENDPOINTS

All efficacy analyses will be performed based on the FAS if not otherwise specified. Selected sensitivity analyses will be performed based on the PPS and will be clearly specified.

15.1. Adjudicated Clinical Endpoints

Clinical events including death (CV or non-CV), nonfatal MI, nonfatal stroke, coronary revascularization, and hospitalization for unstable angina that occurred during the study are reviewed and adjudicated by the CEC in a blinded fashion as described in the Charter.

Positively adjudicated clinical events that occurred after randomization will be summarized by adjudicated event types and subtypes, and by treatment groups for the FAS. They are included in the analyses for the derivation of study endpoints (Sections 3.1, 3.2.1 and 3.2.2).

When a patient had multiple events of the same type (e.g., two coronary revascularizations) on the same day, only one event is counted in descriptive and recurrent event analyses.

All adjudicated deaths and non-fatal clinical events will be presented in listings with information from the adjudication forms.

15.2. Primary Efficacy Endpoint

15.2.1. Primary Efficacy Endpoint

The primary efficacy endpoint is the time to first occurrence of an adjudicated MACE, where MACE is defined as a composite primary efficacy endpoint that includes CV death, nonfatal MI, nonfatal stroke, and coronary revascularization (4-component MACE).

The number of patients who had experienced a primary composite endpoint will be tabulated by the type of the first event and by treatment group. When a patient had multiple events among the 4-component MACE that occurred on the same day, the events will be sorted in the order of: nonfatal MI, nonfatal stroke, coronary revascularization, and CV death.

15.2.2. Primary Analysis Method of Primary Efficacy Endpoint

The null hypothesis, H_0 , is that there is no difference between bempedoic acid 180 mg/day and placebo in time to first occurrence of a confirmed (adjudicated) MACE. The alternative hypothesis, H_1 , is that bempedoic acid 180 mg/day is different from placebo:

$$H_0: \beta = 0 \text{ vs. } H_1: \beta \neq 0$$

Where the hazard $h(t)$ is modeled as: $h(t) = h_0(t)\exp(\beta x)$ and β is the log hazard ratio (HR).

The primary efficacy endpoint will be analyzed using Cox PH model with treatment as a factor. The HR and its 95% CI and p-value from log-rank test will be provided. In addition, KM curves will be provided, to present a graphical description of the time to first occurrence of confirmed adjudicated composite endpoint of CV death, nonfatal MI, or nonfatal stroke (4-component MACE).

If none of these 4-component MACE events is observed, the patient will be censored (Section 7.2.4).

The assumption of proportional hazard will be evaluated graphically for the primary efficacy endpoint by Schoenfeld residual plot and log-log plot. Ad hoc sensitivity analyses may be performed if needed.

15.2.3. Primary Efficacy Endpoint Data Censoring Pattern

For patients who were censored, i.e., did not experience MACE-4 endpoint, the pattern of censoring will be summarized by treatment, including

- censored for non-CV death
- censored on or after completion of the EOS visit during closeout
- censored prior to the study closeout period and not by non-CV death
- censored within 30 days of the last dose
- censored more than 30 days after the last dose

The total patient-year lost-to-follow-up will be calculated by treatment group as the sum of time from the date of censoring prior to study closeout and not by non-CV death, to the May 15, 2022 when the study closeout was initiated.

15.2.4. Sensitivity Analyses of Primary Efficacy Endpoint

In the primary analysis, censoring is assumed to be uninformative, i.e., patients who were censored share a common hazard function as those who were not censored in the same treatment group. However, there is a key difference between them as the censored patients also by definition stopped the treatment, while the majority of those remained on-study were still on-treatment. To evaluate the potential impact, two sensitivity analyses will be performed:

- Multiple imputation analysis: the hazard function for patients after censoring is assumed to be the same as those patients who were assigned the same treatment, had stopped treatment but remained in the study follow-up longer. The data from those patients with follow-up will be used as the model for imputation of the time to events for the censored patients.
- Tipping point (TP) analyses: The goal of this analysis is to explore the plausibility of unobserved data assumptions under which the conclusions change. Unlike the standard multiple imputation analysis, the censored patients in the active treatment group are allowed to have the same or even worse outcome than those in the placebo group. A range of assumed hazard ratios (vs placebo) will be used to evaluate when the estimated treatment effect starts to “tip”, i.e., becoming in favor of the placebo.

The details of the analyses are specified in Appendix 6.

15.3. Analyses of Secondary and Other Efficacy Endpoints

15.3.1. Secondary Efficacy Time-to-Event Endpoints

Each secondary efficacy time-to-event endpoint will be analyzed in a manner analogous to that used for the primary efficacy analysis. For each endpoint, the hazard ratio estimated using Cox

PH model and its 95% CI and associated p-value from log-rank test will be provided. In addition, KM curves will be provided for each of the key secondary efficacy time-to-event endpoints. Note that for the analyses involving hemorrhagic and nonhemorrhagic stroke, any stroke for which the CEC is unable to determine the type will be included as an ischemic (nonhemorrhagic) stroke.

15.3.2. Secondary Efficacy Endpoint Time to NODM

All potential events of NODM are reviewed and verified by the Diabetes Committee in a blinded fashion according to the Diabetes Committee Charter. All events that were reviewed will be presented in a listing. Only verified NODMs are analyzed as efficacy endpoints.

The time to first occurrence of new onset type 2 diabetes mellitus during study will be analyzed by a Cox PH model for the patients with baseline glycemic status (Section 7.4) of no diabetes in the FAS and its subcategories of prediabetes and normoglycemia. The prediabetes subgroup is considered as the primary analysis for this endpoint. The onset date of NODM will be the earliest date of the event as verified by the Diabetes Committee.

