7.2.3. Baseline

For safety parameters, unless otherwise specified, baseline is defined as the last non-missing measurement taken on or prior to Day 1 (including unscheduled assessments).

Baseline for fasting glucose is defined as the mean of the last two non-missing fasting values measured on or prior to Day 1. If only one value is available, then that single value will be used as baseline. Baseline HbA_{1C} is defined as the last non-missing value on or prior to Day 1.

Baseline for lipids parameters (LDL-C, non-HDL-C, TC, HDL-C, TG) is defined as the mean of the last two non-missing fasting values measured on or prior to the *date of randomization*. If only one value is available, then that single value will be used as baseline. If the patient had no fasting values available at baseline, non-fasting values will be used.

Baseline for hs-CRP is defined as the last non-missing value on or prior to the date of randomization.

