8. STATISTICAL CONSIDERATIONS

8.1. Sample Size

This event-driven study is designed to provide at least 90% power to detect an approximate 15% relative risk reduction in hazard ratio corresponding to the primary composite MACE endpoint (CV death, nonfatal MI, nonfatal stroke, or coronary revascularization) at an overall study significance level (alpha) of 0.05. There are no interim efficacy analyses.

A statistical relationship between on-treatment LDL-C differences between the bempedoic acid group and the placebo group and CV event risk reduction is used to derive the postulated treatment effect of 15% stated above. Assuming a 3.59% annual event rate in the placebo group, a minimum of 1620 primary composite MACE events are needed.

The average follow up duration for all patients is estimated to be approximately 42 months (~3.5 years), with an enrollment phase of approximately 33 months, a minimum follow up duration of 24 months (2 years), and a lost-to-follow-up (LTFU) rate of 1% per year. Based on these assumptions, approximately 14,000 patients (approximately 7000 in the bempedoic acid group and 7000 in the placebo group) were randomized into the study to achieve 1620 patients experiencing an adjudicated primary endpoint event.

It is expected that at least 50% of the 1620 patients experiencing an adjudicated primary 4 component MACE (810 patients) will experience an adjudicated 3 component MACE (CV death, nonfatal MI, or nonfatal stroke). Therefore, the study will not stop until at least 1620 patients have experienced an adjudicated primary MACE endpoint, with 810 patients experiencing an adjudicated 3 component MACE, and a minimum of 24 months (2 years) have elapsed since the last patient was randomized.

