8.3. Multiplicity

There are one primary and six key secondary efficacy endpoints of interest for statistical testing in this study. A gatekeeping or hierarchical approach is used to test the primary efficacy endpoint and then key secondary efficacy endpoints sequentially to preserve the study-wise Type I error rate at 5%. For each endpoint, the null hypothesis is that of no difference between bempedoic acid and placebo groups, and the order for the hierarchical testing is:

1. time to first occurrence of MACE (CV death, nonfatal MI, nonfatal stroke, or coronary revascularization; primary 4-component MACE)
2. time to first occurrence of the composite endpoint of CV death, nonfatal MI, or nonfatal stroke (3 component MACE)
3. time to first occurrence of fatal or nonfatal MI
4. time to first occurrence of coronary revascularization

5. time to first occurrence of fatal or nonfatal stroke
6. time to CV death
7. time to all-cause mortality

For the final analysis of the differences between bempedoic acid and placebo, each hypothesis in this hierarchical order will be tested at a two-sided significance level of 0.05. Statistical significance at each step is required in order to test the next hypothesis. If any of the endpoints does not reach statistical significance, p-values for subsequent endpoints will be reported for information only.

For other efficacy and safety endpoints, a nominal p-value may be reported for information only.

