8.6. General Principles

Descriptive statistics (n, mean, standard deviation, median, 1st quartile, 3rd quartile, minimum, and maximum) will be calculated for continuous data as appropriate.

Categorical data will be summarized using counts and percentages. Missing values may be presented as a separate category when appropriate. Counts of zero in any category will be presented without percentage. Ninety-five percent (95%) confidence intervals (CIs) of the means or percentages may be calculated for selected continuous and categorical variables.

For time-to-event endpoints, Kaplan-Meier (KM) curves will be presented graphically by treatment group. KM estimates of cumulative incidence rates at specified time intervals (e.g., month 6, year 1, year 2, and yearly after randomization) and their 95% CIs will be presented. The hazard ratio and its corresponding 95% CI will be estimated from a Cox proportional hazard (PH) model with treatment group in the model. For between-group comparison, p-values (2-sided) will be calculated using log-rank tests.

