15.3.4. Secondary Efficacy Endpoint HbA_{1c}

All efficacy analyses of HbA_{1c} will be carried out stratified by the baseline glycemc status in the FAS. The subgroup of patients with Inadequately Controlled Diabetes (ICDM) at baseline is of primary interest. The other subgroups include Diabetes (that includes ICDM as a subset), Prediabetes, Normoglycemic, and No Diabetes (Prediabetes and Normoglycemic combined).

Analysis for the change from baseline to Month 12 in HbA_{1c} will be analyzed similarly as LDL-C, with change from baseline as response, treatment group and baseline HbA_{1c} as covariates. There is no need to specify variance heterogeneity (no 'REPEATED' statement) and the default method for degrees of freedom calculation can be used. Fitted mean (LS means) changes from baseline for each treatment group will be calculated (with 95% CI) at baseline HbA_{1c} levels of 8% and 7% for ICDM and Diabetes, 6% for Pre-Diabetes and 5.5% for Normoglycemic and the combined No Diabetes groups. The estimated differences in changes from baseline between treatment groups will be provided with 95% CIs and p-values for testing of no difference.

Missing HbA_{1c} data at Month 12 will also be handled using PMM based on whether the patient was still on treatment at Month 12 (Day 365), similar to LDL-C above.

For tertiary endpoints of HbA_{1c} measured at all timepoints (Baseline, Month 3, 6, 12, 18, 24, 30, 36, 42, 48, 54, and 60), the observed values at each timepoint, and changes from baseline will be summarized by treatment groups. Differences of the changes from baseline between the treatment groups will be presented together with 95% CIs at each timepoint, as descriptive analyses with no imputation.

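### The time-to-diabetes Cox model contains treatment only; pre-specifying adjustment for baseline HbA1c and fasting glucose would gain some precision at little cost

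*SAP*

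**What the plan says.** For new-onset type 2 diabetes (NODM), SAP 15.3.2 states: "The time to first occurrence of new onset type 2 diabetes mellitus during study will be analyzed by a Cox PH model". It applies this to patients without diabetes at baseline and to the prediabetes and normoglycemia subsets, with prediabetes as the main analysis. It names no covariates.

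That the model holds treatment only is an inference from three other places:

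- SAP 8.6 says that hazard ratios and their intervals "will be estimated from a Cox proportional hazard (PH) model with treatment group in the model", with p-values from log-rank tests.
- SAP 15.3.1 has secondary time-to-event endpoints follow the primary method.
- SAP 15.2.2 gives that method as a Cox model with treatment as the factor.

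Protocol 15.7.1 likewise names no covariates for NODM. SAP 15.5.2 plans covariate-adjusted Cox models for MACE-4 and MACE-3 only.

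By contrast, SAP 15.3.3 and 15.3.4 include the baseline value in the LDL-C and HbA1c models. The glycemic baselines are already defined. In SAP 7.2.3, "Baseline for fasting glucose is defined as the mean of the last two non-missing fasting values measured on or prior to Day 1", and baseline HbA1c is the last value available by Day 1. The schedule of events collects HbA1c at S1, and safety chemistry, which includes glucose, at S1 and T1.

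**The concern.** SAP 7.4.3 defines NODM mainly by HbA1c of at least 6.5% or fasting glucose of at least 126 mg/dL. How far a patient starts from those limits should therefore be a strong predictor of when the event occurs.

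Restriction to prediabetes narrows that distance but does not remove it. Under SAP Table 1 a patient at 5.7% must rise 6.5 − 5.7 = 0.8 points, and a patient at 6.4% only 0.1. A patient can also qualify on glucose alone, and one fasting value already at or above 126 mg/dL is allowed. The combined No Diabetes model then adds normoglycemic patients with no stated stratification. Protocol 8.3 describes no stratification of randomization by glycemic status.

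Leaving a strong predictor out of a Cox model lowers power and leaves chance imbalance in that predictor inside the treatment estimate. Delay of diabetes in prediabetes is one of the hypotheses in protocol 6.2. SAP 5.3 marks analyses added later as ad hoc, so an adjusted result carries most weight if it is specified now.

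**Working it through.** **1. The plan's own figure.** The only power statement concerns MACE-4. SAP 8.1 says the study is "designed to provide at least 90% power to detect an approximate 15% relative risk reduction in hazard ratio" "at an overall study significance level (alpha) of 0.05", and that "a minimum of 1620 primary composite MACE events are needed". SAP 8.3 gives the sidedness: "each hypothesis in this hierarchical order will be tested at a two-sided significance level of 0.05".

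- Schoenfeld: 4(1.960 + 1.282)² / (ln 0.85)² = 42.03 / 0.02641, giving 1592 events.
- Freedman: (1.960 + 1.282)² × (1.85/0.15)² = 10.51 × 152.1, giving 1599 events.
- Power at 1620 events: 90.5% at HR 0.85 and 96.3% at HR 0.83.

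The 1620 reproduces. The documents give no event rate, effect size or power for NODM, so every NODM input below is an assumption.

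**2. Common assumptions.** 5,600 prediabetic patients (40% of 14,000), 1:1 allocation, follow-up uniform from 2 to 4.75 years. Each simulated trial was analyzed twice: with treatment only, and with treatment plus a baseline covariate.

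**3. Exponential hazards, conditional HR 0.85, 600 trials per row.** The covariate is normal and measured without error. The rate sets placebo incidence at 3.5 years, 1 − exp(−3.5 × rate): 10%, 19% and 30%.

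| Rate/yr | Log HR per SD | HR, treatment only | HR, adjusted | Power, treatment only | Power, adjusted |
|---|---|---|---|---|---|
| 3% | 0.5 | 0.847 | 0.845 | 43.3% | 44.3% |
| 3% | 1.0 | 0.863 | 0.854 | 39.0% | 41.7% |
| 3% | 1.5 | 0.866 | 0.844 | 35.5% | 47.2% |
| 6% | 0.5 | 0.852 | 0.849 | 67.8% | 69.0% |
| 6% | 1.0 | 0.868 | 0.851 | 60.3% | 69.7% |
| 6% | 1.5 | 0.884 | 0.851 | 46.7% | 69.7% |
| 10% | 0.5 | 0.854 | 0.847 | 87.5% | 89.8% |
| 10% | 1.0 | 0.871 | 0.848 | 76.5% | 88.8% |
| 10% | 1.5 | 0.892 | 0.855 | 61.5% | 86.2% |

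The power gain runs from 44.3 − 43.3 = 1.0 point to 86.2 − 61.5 = 24.7 points. The HR moves by 0.00 to 0.04.

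**4. Threshold crossing within prediabetes, 400 trials per row.** True HbA1c has mean 5.85 and SD 0.3, with measurement error SD 0.12. Patients enter with a measured value from 5.7% to below 6.5%. HbA1c drifts upward, and treatment lowers the drift by 0.015 points per year. The event is two consecutive six-monthly values of at least 6.5%. Adjustment uses the measured baseline HbA1c only.

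| Drift mean (SD)/yr | Incidence | Log HR per SD | HR, treatment only | HR, adjusted | Power, treatment only | Power, adjusted |
|---|---|---|---|---|---|---|
| 0.02 (0.08) | 6.0% | 1.22 | 0.779 | 0.766 | 62.7% | 66.0% |
| 0.03 (0.10) | 9.1% | 0.97 | 0.815 | 0.805 | 63.7% | 68.5% |
| 0.05 (0.10) | 11.7% | 0.92 | 0.819 | 0.808 | 71.3% | 78.2% |

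Gains are 3.3, 4.8 and 6.9 points; the HR moves by about 0.01. With 400 trials each power has a standard error of about √(0.65 × 0.35/400) = 2.4 points. The two analyses share the same simulated data, so their differences are better determined than that, but they remain approximate.

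**5. No treatment effect.** Rejection rates, treatment only versus adjusted, were 5.3% vs 4.3% and 6.3% vs 6.4% (exponential, 1,000 trials each) and 4.5% vs 4.8% (threshold, 400 trials). All lie within two simulation standard errors of 5%.

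**6. Chance imbalance.** The standard error of the baseline mean difference is √(2/2800) = 0.027 SD. At a log HR of 1.0 per SD, an imbalance of that size moves the log HR by about 0.027, against |ln 0.85| = 0.163.

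**The case against.** The case for leaving the plan alone is substantial, and several stronger inferences that a reader might draw do not survive it.

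- **That baseline glycemia is ignored.** The main NODM analysis is confined to prediabetes, which Table 1 defines by HbA1c and fasting glucose, and normoglycemia is analyzed separately.
- **That HbA1c is stratified and NODM is not.** SAP 15.3.4 says the HbA1c efficacy analyses "will be carried out stratified by the baseline glycemc status in the FAS", but this means separate subgroup analyses, including a combined No Diabetes group. SAP 15.3.2 does the same. The real contrast is the baseline covariate, and that sits in a linear model.
- **That the hazard ratio is biased.** Its shift toward 1 is non-collapsibility. Under randomization the treatment-only HR is a valid marginal estimate, its test holds its level, and chance imbalance is reflected in its standard error.
- **That this is the sole analysis of the hypothesis.** SAP 15.4.2 adds an on-treatment NODM analysis in the per-protocol set, though it too names no covariates. SAP 16.1.2 has a broader safety definition.
- **That no adjusted NODM analysis exists.** The SAP contents list a section 15.4.4 on additional diabetes analyses whose text is not available here. SAP 7.4.2 mentions an HbA1c sensitivity analysis that no available efficacy section describes, so some diabetes analyses probably lie there.

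The size is also assumed. The exponential model gives the adjusted analysis an error-free predictor, whereas the scheduled baseline HbA1c is one sample about five weeks before randomization.

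All of this limits the point without removing it. The spread within prediabetes remains, and in the available text the main model does not use it.

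**Conclusion.** This is a modest gain in precision that the plan forgoes, and it is not an error. As the available text reads, the NODM Cox model is treatment-only, and the combined No Diabetes model has no stated stratification.

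The most relevant estimate of the loss is about 3 to 7 power points, from the threshold-crossing model within prediabetes. About 1 to 25 points covers the wider range of assumed prognostic strength; the top of that range needs a log HR of 1.5 per SD and a 10% annual rate. Neither range can be derived from the documents. The added value of fasting glucose beyond HbA1c, and the gain from stratifying the No Diabetes model, were not simulated.

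No confirmatory conclusion changes. NODM is outside the testing hierarchy, and both SAP 8.3 and protocol 15.7 treat its p-value as nominal.

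**What to change.** First check that SAP 15.4.4 does not already contain this analysis. If it does not, amend 15.3.2 before unblinding:

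- Pre-specify a Cox model with treatment, continuous baseline HbA1c and continuous baseline fasting glucose, using the SAP 7.2.3 definitions.
- Give that model its own p-value. Otherwise SAP 8.6 and 15.3.1 would pair an adjusted HR with an unadjusted log-rank test.
- In the combined No Diabetes set, stratify the model by prediabetes versus normoglycemia.
- State a rule for a missing baseline covariate.
- Report the treatment-only HR and log-rank p-value beside the adjusted result.

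The cost is a sentence or two of SAP text and one more model, with no new data. The downside is that the adjusted HR is conditional on baseline glycemia and answers a slightly different question, so the two must be labelled conditional and marginal. If the sponsor prefers the marginal HR as the main result, pre-specifying the adjusted model as supportive would still close most of the gap.
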